6.1. Primary Objective

The primary objective of this study is to compare treatment with LY2835219 plus NSAI therapy versus placebo plus NSAI therapy with respect to PFS in postmenopausal women with HR+, HER2- locoregionally recurrent or metastatic breast cancer who have not received prior systemic therapy in this disease setting.

6.2. Secondary Objectives

The secondary objectives of the study are to compare the combination treatment of LY2835219 and NSAI therapy versus placebo plus NSAI therapy with respect to the following:

- OS
- OS rate at 1, 2, and 3 years;
- ORR (CR + PR);
- duration of response (CR + PR);
- DCR (CR + PR + SD);
- CBR (CR + PR + SD \geq 6 months);
- the safety and tolerability;
- change in symptom burden from baseline using the EORTC QLQ-C30, EORTC QLQ-BR23 (breast) questionnaire, and health status scores from the EQ-5D 5L;
- the PK of LY2835219, its metabolites, and NSAI therapy.

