10.1.4. Secondary Efficacy Measures

The following secondary efficacy measures (Table JPBM.10.1) will be collected at the times shown in the Study Schedule (Attachment 1).

Table JPBM.10.1. Secondary Efficacy Endpoints

Endpoint	Definition
Overall Survival (OS)	The time from the date of study randomization to the date of death from any cause
Objective Response Rate	The proportion of patients with CR or PR according to RECIST v1.1
Disease-Control Rate (DCR)	The proportion of patients with CR, PR, or SD according to RECIST v1.1
Clinical Benefit Rate (CBR)	The proportion of patients with CR, PR, or SD ≥6 months according to RECIST v1.1
Duration of Response (DoR)	The time from the date of first evidence of a confirmed CR or PR to the date of objective progression (according to RECIST v1.1) or death from any cause, whichever is earlier

Abbreviations: CR = complete response; PR = partial response; PS = performance status; RECIST = Response Evaluation Criteria in Solid Tumors; SD = stable disease.

Overall Survival (OS): OS duration is measured from the date of randomization of any study drug to the date of death from any cause. For each patient who is not known to have died as of the data-inclusion cutoff date for a particular analysis, OS will be censored for that analysis at the last known alive date.

Objective Response Rate (ORR): The objective response rate is the percentage of patients with a best response of CR or PR.

Duration of Response (DoR): The DoR time is defined only for responders (patients with a confirmed CR or PR). It is measured from the date of first evidence of CR or PR to the date of objective progression or the date of death due to any cause, whichever is earlier. For clarity, the start date should be determined by the initial assessment of CR or PR, not the date of confirmation of CR or PR. If a responder is not known to have died or have objective progression as of the data inclusion cutoff date scores, DoR will be censored at the last complete objective progression-free disease assessment date.

Disease Control Rate (DCR): The DCR is the percentage of patients with a best response of CR, PR, or SD.

Clinical Benefit Rate (CBR): The CBR is the percentage of patients with a best response of CR or PR, or SD for at least 6 months.

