4.2. Secondary Objectives

The secondary objectives of the study are to compare the combination treatment of abemaciclib and NSAI therapy versus placebo plus NSAI therapy with respect to the following:

- overall survival (OS)
- overall survival rate at 1, 2, and 3 years;
- objective response rate (clinical response + partial response [ORR = CR + PR]);
- duration of response (DoR) for CR + PR;
- disease control rate (DCR = CR + PR + stable disease [SD]);
- clinical benefit rate (CBR = CR + PR + SD \geq 6 months);
- the safety and tolerability;
- change in symptom burden from baseline using the European Organization for Research and Treatment of Cancer Quality of Life Questionnaire Core 30 (EORTC QLQ-C30), EORTC QLQ-BR23 (breast) questionnaire, and health status scores from the EuroQoL 5-Dimension 5 Level (EQ-5D 5L);
- the pharmacokinetics (PK) of abemaciclib, its metabolites, and NSAI therapy.

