6.7.4. Other Secondary Endpoints

6.7.4.1. Objective Response Rate, Disease Control Rate, and Clinical Benefit Rate

Objective response rate (ORR), disease control rate (DCR), and clinical benefit rate (CBR) are summary measures of best overall response (BOR) as defined by RECIST v1.1. BOR is derived from time point responses. All time point responses observed while on study treatment and during the short term follow up period (but before the initiation of post discontinuation therapy) will be included in the derivation. The one exception includes patients who receive surgery and/or radiotherapy for locally advanced breast cancer. For these patients, only those time point responses occurring prior to surgery/radiotherapy will be included in the derivation.

Each patient's BOR will be categorized as CR, PR, SD, progressive disease (PD), or not evaluable (NE). For patients with bone-only nonmeasurable disease (see Section 6.4.2), BOR will be limited to CR, SD, PD, and NE. Patients with SD will be further classified as SD \geq 6 months or SD <6 months. Stable disease \geq 6 months includes all patients with a best response of SD and a PFS time of \geq 6 months. A BOR of CR or PR will not require confirmation.

Objective response rate is the proportion of patients with a BOR of CR or PR. Clinical benefit rate is the proportion of patients with a BOR of CR or PR, or SD \geq 6 months. Disease control rate is the proportion of patients with a BOR of CR, PR, or SD. Patients with bone-only nonmeasurable disease cannot have a best response of PR, thus ORR will be reported for both the ITT population and the subset of patients with measurable disease.

For each of these rates, point estimates and confidence intervals (using the normal approximation to the binomial) will be calculated by treatment arm. Stratified tests comparing these rates between treatment arms will be conducted using a Cochran-Mantel-Haenszel (CMH) test.

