6.7.4.2. Duration of Response

The DoR time is defined only for responders (patients with a BOR of CR or PR). It is measured from the date of first evidence of CR or PR to the date of objective progression or the date of death due to any cause, whichever is earlier. It is calculated as date of progression or death – date of first response evaluation of CR or PR + 1. The DoR will be censored according to the same rules as PFS, with the addition of the following rule: if a patient begins post discontinuation therapy, DoR will be censored on the day of the last response evaluation prior to the initiation of post discontinuation therapy.

A KM analysis of DoR will be performed to estimate the DoR curve for each arm. Point estimates and CIs for DoR quartiles and DoR rates will be calculated every 6 months for the first 18 months.

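### Duration of response is listed for comparison between arms, but the only planned analysis is responder-only curves by arm, which is not a randomized comparison (minor; cheap improvement)

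*Protocol*

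**What the plan says.** Protocol 6.2 opens its list of secondary objectives by stating that the study will "compare the combination treatment of LY2835219 and NSAI therapy versus placebo plus NSAI therapy with respect to the following", and the list includes "duration of response (CR + PR". SAP 4.2 keeps the same comparative stem and lists "duration of response (DoR) for CR + PR".

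Protocol 10.1.4 restricts the endpoint: "The DoR time is defined only for responders (patients with a confirmed CR or PR". SAP 6.7.4.2 does likewise: "The DoR time is defined only for responders (patients with a BOR of CR or PR". In both, the clock starts at the first evidence of response.

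The analysis in SAP 6.7.4.2 is by arm: "A KM analysis of DoR will be performed to estimate the DoR curve for each arm", with point estimates and confidence intervals for quartiles and for six-monthly rates over the first 18 months. No log-rank test, hazard ratio, p-value or arm difference is named. Protocol 12.2.7 gives methods for OS and for the response, disease control and clinical benefit rates, but none for duration of response. The alpha scheme in SAP 6.7.3.1 covers PFS and then OS only.

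**The concern.** Responders are selected by something that happens after randomization and that treatment is expected to influence; response rate is itself compared between arms. If the experimental drug produces responses in patients who would not have responded on the aromatase inhibitor alone, its responder group contains two kinds of patient and the control group only one. The difference between the two curves then reflects both the drug's effect on lasting responses and a change in who is counted. It estimates neither cleanly.

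What is at stake is one secondary objective. Medians with confidence intervals, printed by arm under an objective to compare, will be read as a treatment effect unless the plan says otherwise, and no other planned analysis measures time in response over everyone randomized.

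**Working it through.** The documents give no response rate, duration or effect size for this endpoint, so there is no plan figure to reproduce. The calculation shows only how far case mix can move the medians.

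**Inputs**
- Assumed: response rate 35% control, 50% experimental. Every control responder would also respond on the experimental drug, so the added share is (0.50 − 0.35)/0.50 = 0.30 of experimental responders.
- Assumed: exponential durations; control median 18 months; added responders' median *b* = 9 months (12 and 30 as variants).
- Borrowed: the PFS design hazard ratios, 0.714 (Protocol 12.1) and 0.67 (SAP 5.2). Applying either to duration of response in common responders is an assumption.

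**Experimental responder median.** Solve 0.7 × 2^(−t/a) + 0.3 × 2^(−t/b) = 0.5, where *a* = 18/HR.

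| HR in common responders | a | b = 9 | b = 12 | Control |
|---|---|---|---|---|
| 1 | 18.0 | 14.4 | 15.9 | 18.0 |
| 0.714 | 25.2 | 18.1 | 19.9 | 18.0 |
| 0.67 | 26.9 | 18.9 | 20.8 | 18.0 |

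Check of the first cell: 0.7 × 2^(−14.4/18) + 0.3 × 2^(−14.4/9) = 0.402 + 0.099 ≈ 0.50. Check at HR 0.714: 0.7 × 2^(−18.1/25.2) + 0.3 × 2^(−18.1/9) = 0.426 + 0.074 = 0.50.

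- **Reversal.** With HR 1 the experimental curve looks worse although no patient does worse.
- **Dilution.** With HR 0.714 and b = 9, common responders gain 25.2 − 18.0 = 7.2 months, yet the medians differ by 0.1.
- **Exaggeration.** With HR 1 and b = 30 the medians are 20.8 vs 18.0 although common responders gain nothing.

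**How often the median reverses.** A second set of assumptions used a control median of 12 months, response rates of 35–40% vs 45–60%, and HR 0.714. The experimental median falls below control only if the added responders' median is under about 25% of the control median (when they are 20% of responders) to 65% (when they are 42%). For example, rates of 40% vs 60% with b = 4 give 10.0 vs 12 months. At HR 0.67 no reversal occurs with a 20% share.

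**Measure over all randomized patients.** Take a horizon of 24 months from randomization and assume every response starts at month 4, leaving 20 months. Restricted mean duration is g(m) = (m/ln 2)(1 − 2^(−20/m)), so g(18) = 13.95, g(9) = 10.20 and g(25.2) = 15.38. With non-responders at zero:
- Control: 0.35 × 13.95 = 4.9 months.
- Experimental, HR 1: 0.35 × 13.95 + 0.15 × 10.20 = 6.4 months.
- Experimental, HR 0.714: 0.35 × 15.38 + 0.15 × 10.20 = 6.9 months.

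In both cases the contrast favours the arm with more total time in response, where the responder-only medians show a loss or nothing.

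**The case against.** The strongest reply is that the SAP already treats this endpoint descriptively. Where it wants a comparison it says so: for PFS rates (6.7.2.3.1), OS rates (6.7.3.4) and the response-type rates (6.7.4.1). For duration of response it only estimates curves per arm. The comparative stem is generic; it also covers the pharmacokinetics of LY2835219, which a placebo arm cannot supply. Response rate and PFS are compared in all randomized patients, and SAP 6.7.2.3.2 adds a restricted mean difference for PFS, so added responses would not go unseen.

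Most of this stands, and it is why the point is minor. It does not close the gap. Neither document labels the duration curves descriptive, and neither response rate nor PFS measures time spent in response.

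A reader might infer that the plan contains an invalid test, that the responder-only curves will point against the drug, or that the trial's main conclusions are at risk. The documents support none of these. No test is planned. Reversal needs both a response-rate difference and clearly shorter responses in the added responders, and in the main illustration it vanishes once either design hazard ratio is applied to common responders.

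**Conclusion.** The point holds as a minor mismatch between objective and analysis. Duration of response is listed for comparison, the one planned analysis is conditional on a post-randomization event, and no planned analysis gives a randomized answer. The by-arm medians can dilute, exaggerate or, under some assumptions, reverse the difference: 14.4 vs 18.0 months with no effect in common responders, and about equal (18.1 vs 18.0) with a hazard ratio of 0.714. These sizes rest on assumed response rates, assumed exponential durations and borrowed hazard ratios. The lack of a randomized interpretation does not depend on them; it follows from the definition whenever treatment affects who responds. PFS, OS and response-rate conclusions are untouched.

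**What to change.** In SAP 6.7.4.2:

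1. State that the responder-only Kaplan-Meier summaries are descriptive within arm.
2. Add restricted mean time in response over all randomized patients, measured from randomization to a prespecified common horizon, with non-responders counted as zero. It is the area between the Kaplan-Meier curve for PFS and the curve for the first of response, progression or death.
3. Use the same censoring rules for both curves (the PFS rules in Table JPBM.6.1). State how post-discontinuation therapy is handled, since 6.7.4.2 currently censors duration of response at that point and the primary PFS rules do not.
4. Use the SAP's best-overall-response definition of response. SAP 6.7.4.1 says "A BOR of CR or PR will not require confirmation", whereas Protocol 10.1.4 refers to confirmed responders; this choice determines who counts, so the two should be reconciled.
5. Report the arm difference with a bootstrap confidence interval and no alpha. Repeat it in patients with measurable disease, because SAP 6.7.4.1 rules out partial response in bone-only nonmeasurable disease.

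The cost is SAP wording and one program on response, progression and death dates already collected; restricted means are already planned for PFS and OS. The downside is one more, less familiar summary to explain.

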6.3. Exploratory Objectives

- To explore potential biomarkers related to the mechanism of action of LY2835219, the cell cycle, and/or the pathogenesis of breast cancer.
- To explore change in tumor size.

7. Study Population

Individuals who do not initially meet the criteria for participation in this study (screen failure) may be re-screened (Section 7.2.1).

Study participants should be instructed not to donate blood or blood products during the study or for 2 weeks following the last dose of study drug.

Prospective approval of protocol deviations to recruitment and enrollment criteria (also known as protocol waivers or exemptions) is not permitted.

7.1. Inclusion Criteria

Patients are eligible to be included in the study only if they meet all of the following criteria:

- [1] have a diagnosis of HR+, HER2- breast cancer. Although not required as a protocol procedure, metastatic disease should be considered for biopsy whenever possible to reassess HR and HER2 status if clinically indicated.
 - To fulfill the requirement for HR+ disease, a breast cancer must express, by immunohistochemistry (IHC), at least one of the hormone receptors (ER, progesterone receptor [PgR]) as defined in the relevant American Society of Clinical Oncology (ASCO)/College of American Pathologists (CAP) Guidelines (Hammond et al. 2010).
 - To fulfill the requirement of HER2- disease, a breast cancer must not demonstrate, at initial diagnosis or upon subsequent biopsy, overexpression of HER2 by either IHC or in-situ hybridization (ISH) as defined in the relevant ASCO/CAP guidelines (Wolff et al. 2013).
- [2] have locoregionally recurrent disease not amenable to resection or radiation therapy with curative intent or metastatic disease
- [3] have postmenopausal status, defined as meeting one of the following conditions:
 - Prior bilateral oophorectomy
 - Age ≥60 years
 - Age <60 years and amenorrheic (non-treatment-induced amenorrhea secondary to tamoxifen, toremifene, ovarian suppression, or chemotherapy) for at least 12 months. Follicle-stimulating hormone (FSH) and estradiol must be in the postmenopausal range.
- [4] have one of the following as defined by the RECIST v1.1 (Eisenhauer et al. 2009; refer to Attachment 5):
 - Measurable disease

- Nonmeasurable bone-only disease. Nonmeasurable bone-only disease may include any of the following: blastic bone lesions, lytic bone lesions without a measurable soft tissue component, or mixed lytic-blastic bone lesions without a measurable soft tissue component.
- [5] have a PS of ≤ 1 on the ECOG scale (see Attachment 4)
- [6] have adequate organ function, including:
 - hematologic: absolute neutrophil count (ANC) ≥1.5 × 10⁹/L, platelets ≥100 × 10⁹/L, and hemoglobin ≥8 g/dL. Patients may receive erythrocyte transfusions to achieve this hemoglobin level at the discretion of the investigator; however, initial study drug treatment must not begin earlier than the day after the erythrocyte transfusion.
 - hepatic: bilirubin ≤1.5 times the upper limit of normal (ULN) and alanine aminotransferase (ALT) and aspartate aminotransferase (AST) ≤3.0 times ULN (or ALT and AST ≤5 times ULN if liver metastases are present).
 - renal: serum creatinine ≤1.5 times ULN.
- [7] have discontinued previous localized radiotherapy for palliative purposes or for lytic lesions at risk of fracture at least 2 weeks prior to randomization and recovered from the acute effects of therapy (until the toxicity resolves to either baseline or at least Grade 1) except for residual alopecia or peripheral neuropathy.
- [8] are female and \geq 18 years of age
- [9] are able to swallow capsules
- [10] have given written informed consent prior to any study-specific procedures
- [11] are reliable, willing to be available for the duration of the study, and are willing to follow study procedures.

7.2. Exclusion Criteria

Patients will be excluded from the study if they meet any of the following criteria:

- [12] have visceral crisis, lymphangitic spread, or leptomeningeal carcinomatosis. Visceral crisis is not the mere presence of visceral metastases but implies severe organ dysfunction as assessed by symptoms and signs, laboratory studies, and rapid progression of the disease.
- [13] have inflammatory breast cancer.
- [14] have clinical evidence or a history of CNS metastasis. Screening is not required for enrollment.

- [15] are currently receiving or have previously received endocrine therapy for locoregionally recurrent or metastatic breast cancer. [Note: A patient may be enrolled if she received prior (neo)adjuvant endocrine therapy (including, but not limited to anti-estrogens or aromatase inhibitors) for localized disease. In addition, a patient may be enrolled if she has received ≤2 weeks of NSAI in this disease setting immediately preceding screening and agrees to discontinue NSAI until study treatment initiation.]
- [16] have received prior (neo)adjuvant endocrine therapy (e.g., anti-estrogens or aromatase inhibitors) with a disease-free interval ≤12 months from completion of treatment.
- [17] are currently receiving or have previously received chemotherapy for locoregionally recurrent or metastatic breast cancer. [Note: Patients may be enrolled if they received prior (neo)adjuvant chemotherapy for localized disease.]
- [18] have received prior treatment with everolimus
- [19] have received prior treatment with any CDK4/6 inhibitor (or participated in any CDK4/6 inhibitor clinical trial for which treatment assignment is still blinded)
- [20] have initiated bisphosphonates or approved RANK ligand (RANK-L) targeted agents (for example, denosumab) <7 days prior to randomization
- [21] are currently receiving an investigational drug in a clinical trial or participating in any other type of medical research judged not to be scientifically or medically compatible with this study. If a patient is currently enrolled in a clinical trial involving non-approved use of a device, then agreement with the investigator and Lilly clinical research physician (CRP) is required to establish eligibility.
- [22] have received treatment with a drug that has not received regulatory approval for any indication within 14 or 21 days of randomization for a nonmyelosuppressive or myelosuppressive agent, respectively.
- [23] have had major surgery within 14 days prior to randomization to allow for post-operative healing of the surgical wound and site(s).
- [24] have received recent (within 28 days prior to randomization) yellow fever vaccination.
- [25] have serious preexisting medical conditions that, in the judgment of the investigator, would preclude participation in this study (for example, history of major surgical resection involving the stomach or small bowel, or preexisting Crohn's disease or ulcerative colitis).
- [26] have a personal history within the last 12 months of any of the following conditions: syncope of cardiovascular etiology, ventricular tachycardia, ventricular fibrillation, or sudden cardiac arrest.

- [27] have a history of any other cancer (except non-melanoma skin cancer or carcinoma in-situ of the cervix), unless in complete remission with no therapy for a minimum of 3 years.
- [28] have received an autologous or allogeneic stem-cell transplant.
- [29] have active bacterial or fungal infection or detectable viral infection (for example, human immunodeficiency virus [HIV] or viral hepatitis). Screening is not required for enrollment.

7.2.1. Rescreening

A patient who fails screening is allowed to screen again after signing a new informed consent form (ICF) and will be assigned a new patient number under the conditions specified in this section.

The following patients may be eligible for rescreening if any of the following circumstances:

- Patients who have become eligible to enroll in the study as the result of a protocol amendment.
- Patient status has changed such that the eligibility criterion that caused the patient to screen fail would no longer cause the patient to screen fail again.
- Patients who complete screening and meet all inclusion and exclusion requirements but are unable to be enrolled due to extenuating circumstances (such as, severe weather, death in family, childillness).

The investigator should contact the Lilly CRP prior to rescreening a patient.

7.3. Discontinuations

7.3.1. Discontinuation of Patients

The criteria for enrollment must be followed explicitly. If the investigator site identifies a patient who did not meet enrollment criteria and who was inadvertently enrolled, the sponsor must be notified. If the sponsor identifies a patient who did not meet enrollment criteria and who was inadvertently enrolled, the investigator site will be notified. A discussion must occur between the sponsor CRP and the investigator to determine whether the patient may continue in the study, with or without study drug. Inadvertently enrolled patients may be maintained in the study and on study drug when the Lilly CRP agrees with the investigator that it is medically appropriate for that patient. The patient may not continue in the study with or without study drug if the Lilly CRP does not agree with the investigator's determination it is medically appropriate for the patient to continue. The investigator must obtain documented approval from the Lilly CRP to allow the inadvertently enrolled patient to continue in the study with or without studydrug.

In addition, patients will be discontinued from the study treatment (that is, blinded study drug and/or NSAI) and/or from the study in the following circumstances:

• progressive disease (PD) as defined by RECIST v1.1

- enrollment in any other clinical trial involving an investigational drug or enrollment in any other type of medical research judged not to be scientifically or medically compatible with this study
- investigator decision
 - the investigator decides that the patient should be discontinued from the study or study treatment
 - o if the patient, for any reason, requires treatment with another therapeutic agent that has been demonstrated to be effective for treatment of the study indication, discontinuation from the study treatment occurs prior to introduction of the new agent
- patient decision
 - o the patient or the patient's designee (for example, legal guardian) requests to be withdrawn from the study or study treatment
- sponsor decision
 - Lilly stops the study or stops the patient's participation in the study for medical, safety, regulatory, or other reasons consistent with applicable laws, regulations, and good clinical practice (GCP)

The reason and date of discontinuation will be collected for all patients. All randomized patients who discontinue regardless of whether or not they received study drug, will have procedures performed as shown in the Study Schedule (Attachment 1).

